Cover letter

Study protocol

ORIGINAL TITEL:

Comparison between the caudal block and other methods of postoperative pain relief in children undergoing circumcision: A prospective randomized study

Institution review board number (IRB number: 70130623).

Approval date 13\06\2023

The study conforms to the provisions of the Declaration of Helsinki in 1995 (as revised in Edinburgh 2000) and it was ethically approved by the Research Committee for Government Hospitals, Salmaniya Medical Complex, Kingdom of Bahrain (IRB number: 70130623).

Selecting the best analgesia method in pediatrics is so important. This is a randomized a prospective study conducted on 90 children who underwent circumcision. The results showed that circumcision in pediatrics using a caudal block can provide longer analgesia for the patient.

ABSTRACT

Background:

Caudal block (CB), dorsal nerve penile block (DPNB), and systemic opioids are common techniques used in pediatric surgeries to provide analgesia for penile surgery such as circumcision.

Aims: This study aimed to compare the effectiveness of the CB with other methods of postoperative pain release.

Material and Methods: The main operation pediatric theater and post-anesthesia recovery unit (PACU) in the Government Hospitals, Salmaniya Medical Complex, Bahrain.

Study subjects: Successive children aged 3 months to 3 years who had American Society of Anesthesiologists with Physical Status classification one and who had undergone elective circumcision

surgery were recruited., Children were randomized to one of three modalities of intraoperative analgesia: CB, or DPNB. And systemic opioids.

study design: Prospective, Observation-randomized, case-controlled trial study. a study Sample size: all patients, for a total of 90 boys going for circumcision surgery. I was recruited over the course of four months, starting in May 2023. The patients will be divided into three groups: A (CB), B systemic opioids, and C (DPsNB). All patients had operations and were observed, and the three groups were compared based on hemodynamic stability, pain scores, duration of sedation,

analgesia need, and parental satisfaction. where the Face, Leg, Activity, and Cry Consolability s(FLACC) pain scale and behaviors were used to observe and compare the three Groups.

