COVER LETTER

Statistical Analysis Plan

ORIGINAL TITEL:

Comparison between the caudal block and other methods of postoperative pain relief in children undergoing circumcision: A prospective randomized study

This study was approved by the research ethics committee operates Institution Review Board number 70130623

The study conforms to the provisions of the Declaration of Helsinki in 1995 (as revised in Edinburgh 2000) and it was ethically approved by the Research Committee for Government Hospitals, Salmaniya Medical Complex, Kingdom of Bahrain (IRB number: 70130623).

Data management

The collected data were recorded then presented and statistically analyzed by computer using SPSS 27.0 for Windows (*SPSS Inc., Chicago, IL, USA*) and Prism Graphpad version 9.4.1 (*Graphpad, San Diego, USA*). A test of normality was done using the Kolmogorov-Smirnov test. Kruskal-Wallis test was used to compare between groups for numerical variables, while Chi-square and Fisher's Exact test were used for categorical variables. Linear regression analysis was used to detect the predictors of pain scale. All tests were two-sided. The accepted level of significance in this work was ($p \leq 0.05$). A p -value ≤ 0.01 was considered highly statistically significant and $p > 0.05$ was considered non-statistically significant.

Results

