A total of 90 patients had participated in this current study. The study subjects were classified into 3 main groups. The first group (group A) received general anesthesia with caudal block including 29 patients. The second group (Group B) represented general anesthesia with an opioid group with a total of 33 participants, while the last group (Group C) was patients with a penile block 28 patients. Group B was significantly older in comparison with the other two groups, while Group A was the youngest age group as described in Table 1. No significant difference had been observed regarding operation duration among the three groups. Sevo Mac consumption is significantly lower in group A in comparison with the other two groups. Fentanyl consumption intra and post-operative is higher in group B followed by group C, while the lowest level of consumption with among group A patients. Participants' heart rates are shown in Figure 1. Group C significantly showed a higher mean heart rate intraoperative, 5, 10, 20, 30, and 60 minutes postoperative, while group B showed the lowest mean heart rate in the three groups ($p < 0.005$). The behavioral score is represented in figure 2 which had been measured 5, 10, 20, 30, and 60 minutes postoperative. Group C significantly demonstrated a higher percentage of severe discomfort in comparison with the other two groups in 5, 10, 20, and 30 minutes post-operative (82.1, 25.0%, 21.4%, and 3.6% respectively). The percentage of severe discomfort in group B in 5, 10, 20, and 30 minutes post-operative was 18.2, 6.1%, 3.0%, and 0.0% respectively, while only one patient expressed severe discomfort in 5, 10, and 20 minutes in group A. The pain scale was much higher among group C, while group A showed the lowest mean pain scale (Figure 3).

Table 2 represents the crying scale (5, 10, 20, 30, 60 minutes postoperative) among the studied groups. Group C showed a higher percentage of crying in comparison with the other two groups, however, the relation was non-significant.

The movement scale also was significantly different between the 3 groups in 5, 20, and 30 minutes post-operative (Table 3). Similarly, a significant difference was shown between the 3 groups in the agitation scale in 5, 10, and 30 minutes postoperative (Table 4). Table 5, demonstrated a

statistically significant difference between the 3 groups on the posture scale in 5, and 30 minutes post-operative.

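### The protocol concludes that caudal block gives longer analgesia, but the documents report score levels to 60 minutes and fentanyl amounts, not duration

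*Protocol*

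**What the plan says.** The conclusion in the protocol's cover text reads "The results showed that circumcision in pediatrics using a caudal block can provide longer analgesia for the patient". It names no comparator.

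The protocol abstract says that "the three groups were compared based on hemodynamic stability, pain scores, duration of sedation", and adds need for analgesia and parental satisfaction. The only duration in that list is of sedation.

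The SAP (Data management) states that "Kruskal-Wallis test was used to compare between groups for numerical variables". Chi-square and Fisher's exact tests cover categorical variables, and linear regression is used for predictors of the pain scale. No time-to-event method is named.

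On timing, the SAP (Results) states: "The behavioral score is represented in figure 2 which had been measured 5, 10, 20, 30, and 60 minutes postoperative". Crying is tabulated at the same five times (Table 2), and no score is reported after 60 minutes. For severe discomfort under caudal block (Group A) it says that "only one patient expressed severe discomfort in 5, 10, and 20 minutes in group A". The percentages at 5, 10, 20 and 30 minutes are 18.2, 6.1, 3.0 and 0.0 for opioid (Group B) and 82.1, 25.0, 21.4 and 3.6 for penile block (Group C). The Results also say that Group A had the lowest mean pain scale, without giving a time, and that type of block predicted the pain scale at every time from 5 to 60 minutes, without giving a direction. On baseline balance: "Group B was significantly older in comparison with the other two groups".

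**The concern.** A lower score at a fixed time, or a smaller amount of rescue opioid, describes how intense pain was and how much drug was given. Neither says when analgesia ended. A claim of longer analgesia needs a duration, such as the time to first rescue or to a pain threshold, with censoring handled. None is visible here.

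The sentence also merges two comparisons that rest on different evidence. A reader would take it that caudal block outlasted both alternatives. It is the only conclusion stated and stands ahead of the abstract, so it is likely to be carried forward as the trial's finding.

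**Working it through.** **1. Is there a duration outcome?** The abstract's outcome list, the methods under Data management and the Results text were set side by side. They contain scores at fixed times, heart rate, sevoflurane MAC, fentanyl amounts and operation duration. Duration of sedation is listed as compared. Duration of analgesia and time to first rescue appear nowhere.

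**2. Reproducing a stated figure.** Table 2, 60 minutes, not crying / crying: A 17/12, B 19/14, C 12/16. Column shares are 48/90 and 42/90, so expected counts are 15.47, 17.60, 14.93 and 13.53, 15.40, 13.07. Chi-square = sum of (observed - expected)²/expected = 1.799 on 2 df, p = 0.407, as printed.

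**3. Severe discomfort.** Counts from the percentages: B (n=33) 6, 2, 1, 0; C (n=28) 23, 7, 6, 1 at 5, 10, 20 and 30 minutes. Group A is taken as 1/29 at 5, 10 and 20 minutes. No Group A count is stated at 30 minutes, so no contrast is computed there. With d = p1 - p2 and Wilson limits (l, u) for each proportion, the Newcombe limits are:

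- lower = d - √[(p1 - l1)² + (u2 - p2)²]
- upper = d + √[(u1 - p1)² + (p2 - l2)²]

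Penile minus caudal at 5 minutes: p1 = 82.1% (64.4 to 92.1), p2 = 3.4% (0.6 to 17.2), d = 78.7. Lower = 78.7 - √(17.7² + 13.7²) = 56.3; upper = 78.7 + √(10.0² + 2.8²) = 89.1.

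| Contrast | Time | Difference, points (95% CI) | Fisher p |
|---|---|---|---|
| Penile - caudal | 5 min | 78.7 (56.3 to 89.1) | <0.001 |
| Penile - caudal | 10 min | 21.6 (3.1 to 40.1) | 0.025 |
| Penile - caudal | 20 min | 18.0 (0.3 to 36.3) | 0.052 |
| Opioid - caudal | 5 min | 14.7 (-2.0 to 31.2) | 0.11 |
| Opioid - caudal | 10 min | 2.6 (-11.8 to 16.5) | 1.0 |
| Opioid - caudal | 20 min | -0.4 (-14.4 to 12.2) | 1.0 |

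**4. Fentanyl and age.** Inputs are Table 1 means, SDs and group sizes. Welch interval: d ± t × √(s1²/n1 + s2²/n2).

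- Postoperative fentanyl, penile - caudal: 5.2 - 4.8 = 0.4; SE = √(2.5²/28 + 3.1²/29) = 0.745; t = 2.005; 95% CI -1.1 to 1.9. Table 1 lists no A-C pair.
- Postoperative fentanyl, opioid - caudal: 10.5 - 4.8 = 5.7; SE = √(4.6²/33 + 3.1²/29) = 0.986; t = 2.003; 95% CI 3.7 to 7.7.
- Intraoperative fentanyl: penile - caudal 16.4 - 9.9 = 6.5 (3.6 to 9.4); opioid - caudal 22.1 - 9.9 = 12.2 (8.4 to 16.0). Both pairs are listed as significant.
- Age, opioid - caudal: 41.8 - 16.0 = 25.8 months; SE = √(43.3²/33 + 7.5²/29) = 7.66; t = 2.032; 95% CI 10.2 to 41.4. This is approximate, because the Group B SD exceeds its mean.

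All contrasts are unadjusted. Fentanyl units and collection period are not given.

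**The case against.** The case for the sentence is stronger than the absence of a duration outcome suggests. Group A had the lowest mean pain scale, block type predicted pain at all five times including 60 minutes, and intraoperative fentanyl was lower than in both other groups. Other scales still differed at 30 minutes: "The movement scale also was significantly different between the 3 groups in 5, 20, and 30 minutes post-operative", and "a significant difference was shown between the 3 groups in the agitation scale in 5, 10, and 30 minutes postoperative". Posture differed at 30 minutes too. The wording is also hedged (the block *can* provide this). The supplied text lacks the figures and Tables 3 to 6, so recorded rescue times cannot be ruled out.

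Much of this stands as evidence of an advantage within the hour, and a corrected conclusion should say so. It does not reach duration. The pain-scale sentence gives no time. The regression statement and the three-group scale results give no direction or comparator. Even a lower score at 60 minutes would be intensity at one time. The hedge does not help much, since the sentence credits the results with showing it.

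A reader might go further and infer that caudal block does not last longer, or that the groups were equal by 60 minutes. The documents do not support that either. Crying at 60 minutes gives p = 0.407, but the intervals are wide: penile minus caudal 15.8 points (-9.7 to 38.5), opioid minus caudal 1.0 (-22.4 to 24.1). The shrinking gap in severe discomfort does not show the block wearing off, because severe is only the top of four categories and the penile group itself is down to 1/28 by 30 minutes. Nor can one say that the trial's data could never support the claim, because some of the results are not in view.

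**Conclusion.** The concern holds in this form: the stated conclusion is about duration, and the supplied documents contain no duration of analgesia, no time to first rescue, no time-to-event method and no score after 60 minutes. The visible results support lower pain intensity within the hour and less fentanyl, with a different pattern for each comparator:

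- **Versus penile block:** clear early separation in severe discomfort and less intraoperative fentanyl, but no clear difference in postoperative fentanyl.
- **Versus opioid:** clearly less fentanyl during and after surgery, but an imprecise early difference in severe discomfort, and an age imbalance that may confound the comparison.

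The main assumption is the reading of the Group A sentence as one patient at each of the three times. If it means one patient at one time only, Group A is 0/29 at the other two. Any single contrast could then change: penile minus caudal at 20 minutes would become 21.4 (5.2 to 39.5; p = 0.010), or opioid minus caudal at 5 minutes 18.2 (3.1 to 34.4; p = 0.026). The zeros cannot apply at all three times together. Neither reading yields a duration. The Welch intervals are approximations, since the SAP's own test is rank-based.

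**What to change.** Replace *longer analgesia* with lower pain scores within 60 minutes and lower fentanyl amount. State these separately versus penile block and versus opioid, each with an estimate and 95% CI, and give the unclear contrasts alongside the favourable ones. Say that duration of analgesia was not assessed.

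For the opioid comparison, state the age imbalance as a limitation. Group B's mean age of 41.8 months lies above the abstract's upper limit of 3 years (36 months), so check the age data against that limit first. Then add an age-adjusted estimate as a sensitivity analysis.

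Keep *longer* only if times to first postoperative rescue were recorded and a time-to-event analysis, censoring children without rescue at last observation, supports it.

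The cost is a reworded conclusion, contrasts from data already held, and a data check. The time-to-event analysis is needed only if the word is to stay. The downside for the sponsor is a headline less favourable to caudal block.

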Table 6 explains that the type of block, fentanyl intraoperative and postoperative was the predictor of the 5-minute pain scale, while the type of block was only the significant predictor of the 10, 20, and 30-minute pain scale. The type of block and weight of participants were the predictors of the pain scale 60 minutes postoperative

Comparison between the caudal block and other methods of postoperative pain relief in children undergoing circumcision: A prospective randomized study

This study was approved by the research ethics committee operates Institution Review Board number 70130623

Table 1. Demographic data of children who underwent circumcision

Demographic data of children who underwent circumcision Variables	Group A (n=29) Mean±SD	Group B (n=33) Mean±SD	Group C (n=28) Mean±SD	P-value*	Significant pairs**
Age (months)	16.0±7.5	41.8±43.3	16.3±19.7	0.002	Group A vs.s Group B AND Group B vs Group C
Weight (KG)	10.3±2.4	11.3±3.8	9.0±5.1		0.130
Operation duration (minutes)	14.6±3.5	15.1±4.6	16.3±6.1		0.523
Sevo mac	0.5±0.3	2.0±1.6	1.5±0.2	<0.001	Group A vs. Group B AND Group A vs. Group C
Fentanyl intraoperative	9.9±5.4	22.1±9.1	16.4±5.4	<0.001	Group A vs Group B Group A vs. Group C AND Group B vs. Group C
Fentanyl postoperative	4.8±3.1	10.5±4.6	5.2±2.5	<0.001	Group A vs. Group B AND Group B vs. Group C

Comparison between the caudal block and other methods of postoperative pain relief in children undergoing circumcision: A prospective randomized study

This study was approved by the research ethics committee operates Institution Review Board number 70130623

Table 2:

represents the crying scale (5, 10, 20, 30, 60 minutes postoperative) among the studied groups. Group C showed a higher percentage of crying in comparison with the other two groups, however, the relation was non-significant

Crying scale (5, 10, 20, 30, 60 minutes postoperative) among studied groups

Brief title: Participants' Crying Scale

[figure not shown]
Variables	Group A (n=29) N (%)	Group B (n=33) N (%)	Group C (n=28) N (%)	P -value
5 minutes postoperative				
Not crying	19 (65.5)	19 (57.6)	13 (46.4)	0.344
Crying but responds to tender Loving care	10 (34.5)	14 (42.4)	15 (53.6)	
10 minutes postoperative				
Not crying	15 (51.7)	17 (51.5)	10 (35.7)	0.375
Crying but responds to tender Loving care	14 (48.3)	16 (48.5)	18 (64.3)	
20 minutes postoperative				
Not crying	19 (65.5)	16 (48.5)	12 (42.9)	0.200
Crying but responds to tender Loving care	10 (34.5)	17 (51.5)	16 (57.1)	

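### The Group B ages in Table 1 (41.8±43.3 months) cannot come from children aged 3 months to 3 years, and the documents do not explain the conflict

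*Protocol*

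**What the plan says.** The protocol gives the age range once, in the abstract under study subjects: "Successive children aged 3 months to 3 years who had American Society of Anesthesiologists with Physical Status classification one". The study design paragraph of the same abstract describes the sample as "all patients, for a total of 90 boys going for circumcision surgery".

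Table 1 of the SAP has a row for age in months, with columns headed in the form "Group B (n=33) Mean±SD". The entries are 16.0±7.5 for Group A (n=29), 41.8±43.3 for Group B (n=33) and 16.3±19.7 for Group C (n=28), with p=0.002. The pairs marked as different are A versus B and B versus C.

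The SAP Results text agrees with the table: "Group B was significantly older in comparison with the other two groups, while Group A was the youngest age group". The Data management section says how such rows were tested: "Kruskal-Wallis test was used to compare between groups for numerical variables". Neither document mentions a wider age range, enrolment outside the range, a protocol deviation or a data error.

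**The concern.** A mean of 41.8 months is hard to reconcile with a limit of 3 years, and an SD larger than the mean is harder still. The SAP presents the age difference as an ordinary baseline imbalance and does not relate it to eligibility.

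Two things are at stake. The first is the population: until the conflict is resolved, the results cannot be shown to apply to children aged 3 months to 3 years. The second is the comparison with the opioid arm. If the ages are real, contrasts with Group B may mix treatment with age, and the between-group tests named under Data management do not adjust for it. If the ages are mis-recorded, the age row of Table 1 is wrong and its test has to be rerun.

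**Working it through.** **Inputs.** Age range of 3 months to 3 years, from the protocol abstract. Group sizes, means and SDs in months, from SAP Table 1. The group sizes add up: 29+33+28=90. The means and SDs cannot be rebuilt without individual ages, so the check is whether any set of ages in the stated range could produce them.

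**Formulas.** For n ages between a and U with mean m, the largest possible sample SD is √[(m−a)(U−m)·n/(n−1)]. For n=33 and any mean, the maximum occurs with 16 children at one limit and 17 at the other: (U−a)·√[16·17/(33·32)]. Turning the first formula round, the oldest child must be at least m+s²·[(n−1)/n]/(m−a).

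**Group B, limit 36 months.** The mean of 41.8 exceeds 36, which no set of eligible ages allows. The largest SD at any mean is 33·√(272/1056)=16.75. The reported SD is 43.3/16.75=2.6 times that.

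**Group B, limit 48 months.** The mean is possible.
- Largest SD at that mean: √(38.8·6.2·33/32)=15.75; 43.3/15.75=2.7.
- Largest SD at any mean: 45·√(272/1056)=22.84; 43.3/22.84=1.9.

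**Group B, oldest recorded age.** 41.8+43.3²·(32/33)/38.8=41.8+46.9=88.7 months, or 7.4 years. With a lower limit of 0 instead of 3 months it is 85.3 months. Rounding of the reported figures moves these by only about 0.1 month.

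**Group B, how many above the limit.** This depends on the oldest age, which the documents do not give. An exact search found the fewest children above the limit that still reach the reported mean and SD:

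| Assumed oldest age | Minimum of 33 above 36 months | Minimum of 33 above 48 months |
|---|---|---|
| 8 years | 13 | 12 |
| 10 years | 7 | 7 |
| 12 years | 5 | 4 |
| 18 years | 2 | 2 |

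Rounding of the mean and SD by ±0.05 changes none of these counts.

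**Group C.** The largest SD at its mean is √(13.3·19.7·28/27)=16.48 with a 36-month limit and √(13.3·31.7·28/27)=20.91 with 48. The reported 19.7 is impossible under the first and just attainable under the second. The oldest recorded age must be at least 16.3+19.7²·(27/28)/13.3=44.4 months. At least one child must exceed 36 months, and the minimum rises to 3 if the oldest is 60 months and 7 if the oldest is 48. None need exceed 48.

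**Group A.** The largest SD with a 36-month limit is √(13·20·29/28)=16.41, against 7.5 reported, so Group A fits.

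**The case against.** The best defence is that this may be a reporting slip, perhaps a mistyped SD together with a reading of '3 years' that runs to the fourth birthday. In that case the mean of 41.8 could stand and no child need be ineligible. The summary figures cannot exclude this, but it still leaves Table 1 wrong. Damage from PDF conversion is a weaker defence. Other rows of Table 1 are disturbed, but the age row is complete, and both the Results text and the marked pairs agree with its means.

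The SAP also reports openly that Group B was older, and it describes a linear regression for predictors of the pain scale. Some adjustment for age may therefore exist. The Results text names type of block, fentanyl and weight as predictors. Table 6 is not in the text available, so whether age was a candidate is unknown. This limits what can be said about confounding but does not remove the conflict with eligibility.

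Three cautions stand:
- Group C conflicts with the range only under a 36-month limit.
- Group B averages 25.8 months older than Group A (41.8−16.0) but only 1.0 kg heavier (11.3−10.3). That is a reason to check the age entries early. It does not show they are wrong, because neither document gives an expected relation between age and weight.
- The effect of corrections on p=0.002 cannot be predicted. A rank test may move little if a few extreme values change, but more if a dozen do.

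**Conclusion.** The concern holds. Group B's age summary is incompatible with the stated range under every reading: the mean fails with a 36-month limit, and the SD fails with a 48-month limit by a factor of 1.9 to 2.7. The conclusion rests only on the figures being a mean and SD in months for 33 children, as the table labels them. Rounding, the SD divisor and a lower limit of 0 months do not alter it.

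The number of children involved is uncertain because it depends on an assumed oldest age: a minimum of 2 at 18 years, rising to 12 or 13 at 8 years. Three explanations remain open: inclusion outside the range, wrong ages or summary figures, or a wrongly stated range. Each requires a correction. No effect on the pain results has been quantified, and none can be from the documents.

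**What to change.** 1. Verify age and its unit against source for all 90 children.
2. State whether '3 years' means up to 36 months or under 48 months.
3. Report the median, minimum and maximum age per arm and the number of children outside the stated range.
4. Then either correct Table 1 and rerun the age test, or correct the eligibility statement, so that the protocol abstract, the SAP Results text and Table 1 agree.
5. If over-age children are confirmed, keep all 90 randomised children as the main analysis, add a sensitivity analysis restricted to the stated range, and restate the population the conclusion covers. Restriction does not balance age within the range, so give that as a limit of the analysis. Also state whether age was a candidate in the pain-scale regression.

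The cost is a source check of one variable, a small rerun and revised wording. The restricted analysis loses precision: Group B could lose from 2 of 33 children (6%) to 13 of 33 (39%) or more, depending on the ages found.

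### The design statement contradicts itself, no allocation method is described, and the Table 1 age imbalance makes both the allocation record and the age data worth checking before contrasts with Group B are interpreted

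*Protocol*

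**What the plan says.** The title of both documents calls the study randomised. The Protocol abstract gives the design as "Prospective, Observation-randomized, case-controlled trial study".

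The forming of the groups is described in three ways:
- Protocol abstract, study subjects: "Children were randomized to one of three modalities of intraoperative analgesia".
- Protocol abstract, study design: "The patients will be divided into three groups".
- SAP, Results: "The study subjects were classified into 3 main groups".

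Neither document gives a method of sequence generation, an allocation ratio, stratification or concealment.

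On age, the SAP Results state that "Group B was significantly older in comparison with the other two groups". Table 1 gives p=0.002, with A vs B and B vs C as the significant pairs. The Protocol abstract limits entry to ages 3 months to 3 years.

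Under Data management, the SAP compares groups with Kruskal-Wallis, chi-square and Fisher's exact tests. It adds a linear regression for predictors of the pain scale, without listing covariates. The Protocol's opening summary concludes that caudal block can give longer analgesia.

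**The concern.** An observational study does not assign treatment, a randomised trial does, and a case-control study selects subjects by outcome. Which label is true decides whether a difference between groups can be read as an effect of the block.

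The documents assert randomisation but do not describe it, so a reader cannot settle the matter from the text. The one baseline variable that differs significantly is age, and it differs by a lot. If children reached the opioid group by age or by clinician choice, the unadjusted comparisons of pain, heart rate and fentanyl totals with that group would mix the effect of the technique with the effect of age. The title and the causal conclusion would then claim more than the design supports.

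**Working it through.** **Inputs.** Group sizes 29, 33 and 28 (SAP, Results). Age in months: A 16.0±7.5, B 41.8±43.3, C 16.3±19.7. Weight in kg: A 10.3±2.4, B 11.3±3.8, C 9.0±5.1, p=0.130 (SAP, Table 1). Eligible age 3 to 36 months (Protocol abstract).

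**1. The reported age p-value.** Kruskal-Wallis needs individual ages, so 0.002 cannot be reproduced exactly. It can be bracketed from the summary data.
- Grand mean = (29×16.0 + 33×41.8 + 28×16.3)/90 = 25.55.
- One-way ANOVA: between-group mean square 13,754.7/2 = 6,877.3; within-group mean square 72,049.9/87 = 828.2; F = 8.30, p=0.0005.
- Welch ANOVA: F = 5.59, p=0.007.

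The stated 0.002 lies between the two. Kruskal-Wallis tests on simulated ages with the stated means and SDs gave a median p of 0.002 for gamma-shaped ages and 0.00003 for lognormal ages. Both shapes are assumptions.

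**2. Pairs (Welch t-tests).**
- A vs B: difference 25.8, standard error √(7.5²/29 + 43.3²/33) = 7.67, t = 3.37, p=0.002. Standardised difference 25.8/√((7.5²+43.3²)/2) = 25.8/31.07 = 0.83.
- B vs C: difference 25.5, standard error 8.41, t = 3.03, p=0.004. Standardised difference 0.76.
- A vs C: difference 0.3, standard error 3.97, p=0.94.

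These agree with the significant pairs in Table 1.

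**3. Size of the gap.** 41.8 − 16.0 = 25.8 months, and 25.8/16.0 = 1.6 times A's mean.

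**4. How unusual under randomisation.** For one variable, p≤0.002 has probability 0.002, or 0.2%. For the smaller of two independent baseline p-values (age and weight) it is 1 − 0.998² = 0.4%.

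**5. Group sizes.** Against 30/30/30 (1:1:1 is an assumption, as no ratio is stated), chi-square = (1 + 9 + 4)/30 = 0.47, p=0.79. The sizes give no evidence against randomisation.

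**6. Are the ages possible within eligibility?**
- B's mean of 41.8 is above the 36-month limit.
- For any 33 values in 3 to 36, the largest sample SD is 16.5×√(33/32) = 16.8; the table gives 43.3.
- For 28 values in that range with mean 16.3, the largest SD is √((36−16.3)(16.3−3))×√(28/27) = 16.5; the table gives 19.7.
- If no child in B was under 3 months, an SD of 43.3 needs a recorded age of at least 41.8 + (43.3²×32/33)/(41.8−3) = 41.8 + 46.9 = 88.7 months.

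So B and C each contain at least one recorded age outside 3 to 36 months, or the printed figures are wrong.

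**7. Weight as a cross-check.** B exceeds A by 1.0 kg (Welch p=0.22), about 10% of A's mean, while its mean age is 161% higher.

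**8. Adjustment.** For the pain scale, the SAP Results name type of block and fentanyl (5 minutes), type of block (10, 20 and 30 minutes), and type of block and weight (60 minutes). Age is not named. The regression table itself is not in the text available, so age may have been entered and found non-significant, or never entered.

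**The case against.** The strongest reply is that the age row is too unreliable to say anything about allocation. The B and C figures conflict with the eligibility range, and weight hardly differs between A and B. If the cause is a unit or entry error, the p-value carries no information about randomisation. This stands as a rival explanation. It does not clear the design statement, which is contradictory whatever the ages are, and it makes checking the ages the first step.

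A second reply is that age cannot explain the most striking result. Severe discomfort at 5 minutes was seen in one Group A patient (1/29 = 3.4%) against 82.1% of Group C, and A and C have almost the same mean age. This stands at the level of means, although C's spread is wider. The confounding concern mainly touches contrasts with B.

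A third reply is that the SAP already has a regression in which type of block is a predictor at every time point. This stands too: what is missing is a statement of whether age was in the model.

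A reader might infer that the children were not randomised at all. The documents do not support that. They state randomisation in the title and text, the group sizes fit equal allocation, and a small baseline p-value can arise by chance or from bad data. A reader might also take *case-controlled* as a loose term for *controlled*; even so, *observation* still conflicts with *randomized*.

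**Conclusion.** The point holds in a limited form. The design labels conflict and the allocation method is not described; both are plain from the text. The age difference of 25.8 months (standardised difference 0.83 for A vs B) would be unusual under sound randomisation, at about 0.2% for one variable or 0.4% for the smaller of two. It is a reason to check the allocation record, not proof that allocation failed. Ineligible children or wrong age data could equally lie behind it.

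Contrasts with Group B may be confounded by age, and the documents do not show that age was adjusted for. The A vs C contrast is little affected as far as mean age goes. This rests on taking the Table 1 means and SDs as printed. The 0.4% figure also assumes that age and weight are independent, which is a simplification.

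**What to change.** In this order:

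1. Check individual ages against source records and the 3 to 36 month range. Correct errors and flag children outside the range.
2. Reconcile the design statement with the allocation record. If a random sequence was used and followed, delete *observation* and *case-controlled* and describe how the sequence was generated and concealed. If not, delete *randomized* from the title and text, report a prospective non-randomised comparison, and weaken the causal conclusion.
3. State whether age was entered in the existing pain-scale regression. With verified ages, include it and report age-adjusted group contrasts, at least for A vs B and B vs C, beside the unadjusted tests, and again within the eligible age range. If allocation was not random, make the adjusted contrasts the main result. If it was, they can stand beside the unadjusted tests, since a covariate chosen after a significant baseline test is a data-driven choice.

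The cost is a check of existing records, some rewording and an extension of a model already in the SAP, with no new data collection. The downsides are that the design claim may have to be weakened and that adjustment is imprecise where the groups' ages do not overlap.
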